4.2.3. Sensitivity analyses

Sensitivity analyses on the priors (in particular the prior for the between-participant and within pa SD) will be carried out.

4.3. Secondary Pharmacodynamic Analyses

4.3.1. Definition of endpoint

Wheal response related endpoints (parts 1 and 2):

The following endpoints will be calculated at challenge visit 1 (parts 1 and 2) and challenge visit 2 (part 2) using the wheal area (mm^2) determined by the calliper method (see OPS) and for each of the skin challenges:

- Wheal response-time area under the curve (AUC) over the 2h post-challenge period
- Maximum observed wheal area (mm^2) during the 2h post-challenge period.
- Time (min) to maximum observed wheal area during the 2h post-challenge period

- Time (min) of complete wheal area disappearance during the 2h post-challenge period. The complete disappearance is defined as a wheal area of 0. If the complete disappearance does not occur within the 2h post-challenge period, the time will be set to >120min.

The longest and orthogonal diameters (mm) of the wheal, measured by the calliper method, will also be summarised by challenge visit and skin challenge in the same way:

- Maximum observed wheal longest/orthogonal diameter (mm) during the 2h post-challenge period.
- Time (min) to maximum observed wheal longest/orthogonal diameter during the 2h post-challenge period
- Time (min) of complete wheal longest/orthogonal diameter disappearance during the 2h post-challenge period. The complete disappearance is defined as a wheal longest/orthogonal diameter of 0. If the complete disappearance does not occur within the 2h post-challenge period, the time will be set to >120min.

Flare response related endpoints (part 1 and 2)

The following endpoints will be calculated at challenge visit 1 (parts 1 and 2) and challenge visit 2 (part 2) using the flare area (mm^2) as determined by the calliper method (see OPS).

- Flare response-time area under the curve (AUC) over the 2h post-challenge period
- Maximum observed flare area during the 2h post-challenge period.
- Time (min) to maximum observed flare area during the 2h post-challenge period
- Time (min) of complete flare area disappearance during the 2h post-challenge period. The complete disappearance is defined as a flare area of 0. If the complete disappearance does not occur within the 2h post-challenge, the time will be set to >120min.

The longest and orthogonal diameters (mm) of the flare, measured by the calliper method, will also be summarised by challenge visit and skin challenge in the same way:

- Maximum observed flare longest/orthogonal diameter (mm) during the 2h post-challenge period.
- Time (min) to maximum observed flare longest/orthogonal diameter during the 2h post-challenge period
- Time (min) of complete flare longest/orthogonal diameter disappearance during the 2h post-challenge period. The complete disappearance is defined as a flare longest/orthogonal diameter of 0. If the complete disappearance does not occur within the 2h post-challenge period, the time will be set to >120min.

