#### **4.3. Justification for Substance P concentrations**

Published data indicate that the wheal and flare responses to intradermal SP continue to increase with increasing concentrations, even up to 100  $\mu\text{mol/L}$  [Zirbs, 2013]. However, at the cellular level in an in-vitro mast cell line, SP begins to exert effects at  $\sim 0.1 \mu\text{mol/L}$  and the effect plateaus at  $\sim 10 \mu\text{mol/L}$ . The probable reason for the result in human skin is as the concentration of SP increases, it diffuses to a larger area of the dermis, causing larger reactions by activating more mast cells. To avoid concentrations of SP that are well above maximum effectiveness, the human mast cell line data were used to determine the SP concentrations in this study. Concentrations of 0.1, 0.3, 1 and 3  $\mu\text{mol/L}$  SP are expected to give a range up to  $\sim 95\%$  of the maximum effect at the cellular level. Those concentrations have been shown to cause wheal and flare responses when given intradermally to healthy people [Borici-Mazi, 1999; Grouzmann, 2011; Sabroe, 1997; Zirbs, 2013].

To allow for possible differences between published data and our SP challenge model, the concentrations of SP may be changed during the study in order to elicit the desired wheal response. For example, if the wheal response following one or more SP concentrations was indistinguishable from the wheal response following saline, and/or the wheal response was indistinguishable between 2 concentrations of SP, the concentrations could be adjusted accordingly. The maximum amount of SP administered in a single injection will not exceed 50  $\mu\text{L}$  of 10  $\mu\text{mol/L}$ .

The SP concentrations administered in Part 2 will be selected to ensure that the lowest concentration gives a wheal response larger than the wheal response following saline, and that each increasing concentration gives a wheal response larger than that at the previous concentration.

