#### Type of Participant and Disease Characteristics

2. Participants who are overtly healthy as determined by medical evaluation including medical history, physical examination, laboratory tests, ECGs and vital signs.
3. Participants who responded positive to histamine skin prick test and negative to saline injection at screening.
4. Participants with Fitzpatrick skin type I-II (Caucasian).

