6.2.4. Assessment Window

No Assessment Windows will be defined for analysis, and all (except Safety) summaries and analyses will be based on nominal visits. Safety summaries and analyses will use the remapped visits. Please see OPS for further details.

Unscheduled and withdrawal visits will not be slotted to an analysis timepoint, but they will be considered for worse case and maximum displays. If multiple assessments qualify for worse case or maximum, the earlier one will be used.

Acceptable windows are included in the SRM and assessments performed within these windows are not protocol deviations.

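### SAP 4.3.1 has no rule for a site that never responds, so its disappearance time is either 5 min or >120 min and its time to maximum is undefined

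*SAP*

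**What the plan says.** SAP 4.3.1 calculates the wheal endpoints at each challenge visit "and for each of the skin challenges". SAP 4.2.1 names saline and histamine as control challenges alongside each Substance P (SP) concentration, so saline sites are included.

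- **Disappearance.** For wheal, "The complete disappearance is defined as a wheal area of 0". For flare, "The complete disappearance is defined as a flare area of 0". The longest and orthogonal diameters are treated the same way.
- **The one special case.** "If the complete disappearance does not occur within the 2h post-challenge period, the time will be set to >120min".
- **Time to maximum.** The endpoint is "Time (min) to maximum observed wheal area during the 2h post-challenge period", with no condition that the maximum exceeds 0.
- **Ties.** SAP 6.2.4, on assessment windows, says "If multiple assessments qualify for worse case or maximum, the earlier one will be used". The sentence before it concerns unscheduled and withdrawal visits.

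The missing-data rules in SAP 6.2.7 do not mention a site without a response. SAP 4.3.2.3 limits the time endpoints to descriptive statistics and graphs. By SAP 4.1.1 these include the mean, SD, median, interquartile range, minimum and maximum.

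**The concern.** A disappearance time means something only if a response was there to disappear, and SAP 4.3.1 does not make that a condition. The same all-zero record can be given the shortest possible time or the longest category, depending on how a programmer reads one sentence. Neither value describes that site.

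The rule also misfires for sites that do respond. A zero before a late-onset peak, or a single zero between positive readings, meets the definition. The first case can give a disappearance time earlier than the site's own maximum.

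The time course at each concentration is a named secondary objective in both parts. Absent responses are most plausible at saline and the lowest concentrations. If their share changes with concentration, summaries of speed and duration could shift with it even where the responders' time course is the same.

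**Working it through.** The plan gives no figure for these endpoints, so there is none to reproduce. The check applies the SAP rules literally to response profiles on the protocol's reading times.

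**Inputs from the documents**
- Readings at 5, 10, 15, 20, 40, 60, 90 and 120 min (Protocol 1.3.3).
- Up to 12 participants in Part 1 and up to 20 in Part 2 (SAP 5).
- Literal rules: disappearance is the first reading with area 0, or >120 min if there is none. The maximum is the earliest of tied readings, if SAP 6.2.4 is taken to apply.

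**Assumptions, not in the documents**
- Responders peak at 15 min and first read 0 at 90 min.
- The share p of all-zero sites ranges from 0% to 75%.

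**Step 1: single sites**

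| Profile (mm² at the eight readings) | Time to maximum | Disappearance, literal | Disappearance, first 0 after the maximum |
|---|---|---|---|
| 0 throughout | 5 (tie rule) or undefined | 5 | no response |
| 20, 40, 60, 50, 30, 10, 0, 0 | 15 | 90 | 90 |
| 0, 10, 30, 40, 30, 10, 0, 0 | 20 | 5 | 90 |

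The third site is recorded as cleared 15 min before its peak (20 − 5).

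**Step 2: group summaries if all-zero sites are coded 5 min**

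Mean time to maximum = (1 − p) × 15 + p × 5. Mean disappearance = (1 − p) × 90 + p × 5.

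| All-zero sites of 20 | Mean (median) time to maximum | Mean (median) disappearance |
|---|---|---|
| 0 (0%) | 15.0 (15) | 90.0 (90) |
| 2 (10%) | 14.0 (15) | 81.5 (90) |
| 5 (25%) | 12.5 (15) | 68.8 (90) |
| 10 (50%) | 10.0 (10) | 47.5 (47.5) |
| 15 (75%) | 7.5 (5) | 26.2 (5) |

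With 12 participants the 25%, 50% and 75% rows are the same. One all-zero site of 12 gives means of 14.2 and 82.9 min. If responders instead clear at 60 min, the mean disappearance at 25% is 0.75 × 60 + 0.25 × 5 = 46.3 min, and at 50% it is 32.5 min.

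**Step 3: the other coding**

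If all-zero sites are coded >120 min, SAP 4.3.1 does not say what number enters a mean. Taking 120 as a lower bound, the mean is at least (1 − p) × 90 + p × 120: 97.5 min at 25% and 105 min at 50%. The two codings differ by at least p × (120 − 5), which is 28.8 min at p = 25%, in opposite directions from the responders' 90 min.

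**Step 4: after the fix**

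All-zero sites contribute no time. The summaries stay at 15 and 90 min at every p, on 9 of 12 or 15 of 20 sites when p = 25%.

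**The case against.** Several stronger readings are tempting, and the documents do not support them.

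- **That the SAP fixes the time of maximum at 5 min.** The tie rule follows text on unscheduled and withdrawal visits and is not stated for pharmacodynamic endpoints. All that is established is that the time to maximum of an all-zero site has no clear definition.
- **That all-zero sites are known to be common.** Entry is for "Participants who responded positive to histamine skin prick test and negative to saline injection at screening", but the acceptable control responses are defined in the Study Reference Manual, and a negative response need not mean area 0 at all eight readings. Protocol 4.3 considers adjustment "if the wheal response following one or more SP concentrations was indistinguishable from the wheal response following saline", which is not the same as no wheal. Protocol 2.3.1 and 6.1 do contemplate an absent response, but only as grounds for using higher concentrations. Protocol 4.3 also says the starting concentrations have produced wheal and flare in healthy people, and it selects the lowest Part 2 concentration to exceed saline.
- **That a false concentration trend is shown, or that the Part 2 sampling window rests on these times.** The first needs non-responder shares that the documents do not give. The second is not stated: Protocol 4.2 refers to review of Part 1 wheal data generally.

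It is also fair to say that the Output and Programming Specification is not available and might hold a rule, that maximum area is summarised alongside and would reveal absent responses, and that medians barely move until about half the sites are non-responders. Calling an absent wheal very short can be defended, while a responder-only summary conditions on a post-challenge outcome.

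These points limit the size of the problem but do not remove it. The disappearance definition is written in the SAP itself. Arguing that disappearance implies a prior response only moves the same site from 5 min to >120 min.

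**Conclusion.** The point holds as a defect in a stated derivation rule. A site with no response can be coded at either extreme for disappearance, its time to maximum is not clearly defined, and a zero before or between positive readings can pass as disappearance.

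The effect is confined to descriptive secondary time endpoints for wheal and flare. It falls mainly on means, and mainly at saline or low concentrations. The primary AUC and its models are untouched, because an area of 0 is a valid contribution to an AUC.

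The size is unknown, since the share of all-zero sites is not given. The illustrative shifts (at 25% coded 5 min, 15 to 12.5 min and 90 to 68.8 min in the means, none in the medians) rest on assumed responder times and shares. The SAP should be corrected, but the main conclusions of the study do not depend on it.

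**What to change.** In SAP 4.3.1, for wheal and flare and for areas and diameters:

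1. Derive time to maximum and time of disappearance only when at least one post-challenge value exceeds 0. Otherwise record 'no response'.
2. Define disappearance as the first 0 after the time of maximum with no later non-zero value.
3. Keep >120 min only for responses still present at 120 min, and state how that category enters the summaries.
4. State whether the SAP 6.2.4 tie rule applies to time to maximum.
5. Report the number and percentage of sites with no response beside each summary, by challenge and visit.

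The cost is a few lines of SAP text and a small programming change, with no new data collection. The price is a smaller n where non-response occurs, and summaries conditional on having responded. These compare different subsets of participants across concentrations, so the SAP should say that they must be read together with the non-responder counts.

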4.3.2. Main Analytic approach

4.3.2.1. Summary Measure

The summary measure is the difference in flare response AUC between 2 consecutive SP concentrations at challenge visit 1 (parts 1 and 2) and at challenge visit 2 (part 2).

4.3.2.2. Population of interest

The secondary pharmacodynamics analyses will be based on the Safety population, unless otherwise specified.

4.3.2.3. Statistical Analyses

Endpoints / variables defined in Section 4.3.1 will be summarised using descriptive statistics, and graphically presented (where appropriate).

The proposed statistical analyses planned for the primary PD endpoint (Section 0) will be repeated for the flare response-time area under the curve (AUC) over the 2h post-challenge period for parts 1 and 2.

For the other endpoints, no statistical analyses will be carried out.

4.4. Exploratory Biomarker Analyses

The exploratory biomarker analyses will be based on the Safety population and will be reported for part 2 only.

No formal statistical testing will be performed on biomarkers data.

Histamine concentrations (ng/mL) from intradermal microdialysis during the 2h post-challenge will be summarised using descriptive statistics and graphically presented (where appropriate) at challenge visits 1 and 2 of part 2 in a similar way as the wheal and flare responses.

Additional biomarker analyses of the skin punch biopsies and blood samples (visit 2 only) may be conducted. These results will be the subject of a post hoc analysis.

4.5. Safety Analyses

The safety analyses will be based on the Safety population. No formal statistical testing will be performed on safety data.

Displays will be generated for parts 1 and 2, separately (but in the same file) and for the study intervention group “Skin Challenges”.

4.5.1. Extent of Exposure

A listing of exposure to skin challenges (intervention) will be produced for each subject based on location, laterality and directionality for the skin challenges, concentration ($\mu\text{mol/L}$), volume (μL) and dose (pmol)

For the SP challenges, the dose (pmol) will be derived from the concentration and volume (see OPS).

4.5.2. Adverse Events

An adverse event (AE) is defined as a study intervention emergent AE if it is an AE that started on or after the date/time of first study intervention

An AE is not a study intervention emergent AE if it started and ended before the date/time of first study intervention.

All AE summaries will be based on study intervention emergent events unless otherwise specified. SAE summaries will be based on all SAEs reported regardless of whether they meet the definition of study intervention emergent or not. All AE and SAE summaries will be by PT only unless otherwise specified.

Adverse events will be coded using the standard Medical Dictionary for Regulatory Affairs (MedDRA dictionary).

Summary tables will include the number of participants with the AE, the percentage of participants with the AE. The following AE categories will be provided:

- All adverse events by SOC, PT and maximum intensity
- Common non-serious AEs by SOC and PT (Number of Subjects and Occurrences):
 - For disclosure purposes, common is defined as AEs occurring in at least 5% of any intervention arm. Due to the small sample size of this study this table will include all non-serious AEs.
- AEs related to study intervention by SOC, PT and maximum intensity:
 - A study intervention-related AE is defined as an AE for which the investigator classifies the possible relationship to study interventions as “Yes”. A worst-case scenario approach will be taken to handle missing data, i.e. the summary table will include events with the relationship to study intervention as ‘Yes’ or missing.
 - The summary will be generated for the relationship to SP only, histamine only, and both SP and histamine, separately.
- SAE by SOC, PT and maximum intensity
- SAE by SOC and PT (Number of Subjects and Occurrences)
- Serious fatal and non-fatal study intervention related AEs by overall frequency

4.5.2.1. Adverse Events of Special Interest

Not applicable.

4.5.2.2. COVID-19 Assessment and COVID-19 AEs

It is the investigator who decides whether an AE is a COVID related Adverse event or not.

Listings will be produced for subjects with COVID-19 Adverse Events.

4.5.2.3. Impact of COVID-19 Pandemic on Safety Results

The impact of the COVID-19 pandemic on the safety results will be assessed, if any.

4.5.3. Additional Safety Assessments

4.5.3.1. Laboratory Data

Summary tables for haematology and chemistry laboratory tests as well as urine concentration parameters will be produced:

- Change from baseline in laboratory parameters (clinical chemistry and hematology) will be presented for continuous variables, with a summary of baseline values included in the tables.
- Summaries of worst-case results post-baseline relative to baseline will be provided for the following tests:
 - For lab tests with associated Potential Clinical Importance (PCI) criteria: the summary will include baseline data and worst-case post-baseline. The baseline categories are: Low, W/in Range and High. The change categories are: To Low, To w/in Range or No Change, To High. If a subject has a decrease to low and an increase to high during the same time interval, then the subject is counted in both the “to Low” and the “to High” categories.
 - For categorical urinalysis parameters

For part 2, change from baseline will be calculated for each visit, (using the visit 1 baseline for visit 1, and visit 2 baseline for visit 2).

Baseline and post-baseline data will be included in these tables. If a participant moves to both a low and a high clinical concern range during the study intervention period, then the participant is counted in both categories.

Summaries of hepatobiliary laboratory events including possible Hy's law cases will be provided in addition to what has been described above. Possible Hy's law cases are defined as any elevated alanine aminotransferase (ALT) $>3\times$ upper limit of normal (ULN), total bilirubin $\geq 2\times$ ULN and alkaline phosphatase (ALP) $<3\times$ ULN/missing. Total bilirubin $\geq 2\times$ ULN can be within 28 days following the ALT elevation and if direct bilirubin is available on the same day, it must be $\geq 35\%$ of total bilirubin.

ALP $<3\times$ ULN/missing means it is satisfied unless the ALP is $\geq 3\times$ ULN at the time of bilirubin elevation. The summary will be produced for worst case post baseline only.

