### 1.3.2. Part 1 & Part 2 Challenge Visits

Visit (V)	V1, V2 (Part 2 only)					Follow-up phone call (5-7 days post last challenge day)	Early withdrawal	Notes
Procedure	Pre-challenge	Within 1 h before first control challenge	At least 20 min before first SP challenge	SP challenges	2 h after last SP challenge			
Clinical chemistry/Haematology and urinalysis		X			X*		X	*In Part 2, 2 h post last SP challenge at last challenge visit only.
12-lead ECG		X			X		X	Triuplicate measurements.
Vital signs		X			X		X	Refer to Section 8.2.2.
Brief PE		X						
Urine pregnancy test (WCBP only)	X							
Visual check of planned challenge sites	X							Prior to any other study procedures.
Saline and Histamine challenges			X					Histamine to be administered at least 20 cm from any IDM sampling
SP challenge				X				Part 1: Up to 4 SP injections: increasing concentrations of SP at a minimum of 20-min intervals. Part 2: Up to 10 SP injections: 

• up to 4 increasing concentrations of SP at a minimum of 20-min intervals, in duplicate

Visit (V)	V1, V2 (Part 2 only)					Follow-up phone call (5-7 days post last challenge day)	Early withdrawal	Notes
Procedure	Pre-challenge	Within 1 h before first control challenge	At least 20 min before first SP challenge	SP challenges	2 h after last SP challenge			
								
 
• a further 2 SP injections at one concentration may also be given, if ongoing data suggest biopsy samples are required
 

Wheal and flare assessment		See Section 1.3.3						
Blood sample for exploratory biomarkers		X			X			Part 2, V2 only.
IDM		See Section 1.3.3						Part 2 only
Skin punch biopsy		See Section 1.3.3						Part 2, V2 only. May or may not be performed based on ongoing data.
AE review		<===== =====>					X	
SAE review		<===== =====>					X	
Concomitant medication review		X						Review of medications since last visit, if applicable.
Follow-up on possible reactions at sites of IDM/biopsy						X		Part 2 only.

Abbreviations: AE = adverse event; ECG = electrocardiogram; IDM = intradermal microdialysis; SAE = serious adverse event; SP = substance P.

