## **8. STUDY ASSESSMENTS AND PROCEDURES**

- Study procedures and their timing are summarized in the SoA.
- Protocol waivers or exemptions are not allowed
- Immediate safety concerns should be discussed with the sponsor immediately upon occurrence or awareness to determine if the participant should continue or discontinue study intervention.
- Adherence to the study design requirements, including those specified in the SoA, is essential and required for study conduct.
- All screening evaluations must be completed and reviewed to confirm that potential participants meet all eligibility criteria. The investigator will maintain a screening log to record details of all participants screened and to confirm eligibility or record reasons for screening failure, as applicable.
- Procedures conducted as part of the participant's routine clinical management (e.g., blood count) and obtained before signing of ICF may be utilized for screening or baseline purposes provided the procedure met the protocol-specified criteria and was performed within the time frame defined in the SoA.
- The maximum amount of blood collected from each participant over the duration of the study, including any extra assessments that may be required, will not exceed 500 mL.
- Repeat or unscheduled samples may be taken for safety reasons or for technical issues with the samples.

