4.1.2. Baseline Definition

For part 1, there will be 1 baseline value (baseline visit 1). For part 2, there will be 2 baseline values, one for each visit (baseline visit 1 and visit 2).

For the PD endpoints (wheal and flare responses), the baseline value will be the saline control non-missing value pre-SP challenge at challenge visit 1 and challenge visit 2 (parts 1 and 2). No missing baseline values will be allowed as part of the inclusion/exclusion criteria.

For the other endpoints collected at challenge visits 1 and 2, the baseline value will be the latest non-missing pre-1st control challenge assessment value at challenge visit 1 and challenge visit 2 (parts 1 and 2), including those from unscheduled visits.

For Part 2, the Baseline for Visit 2 will be the latest assessment performed after Visit 1 visits (such as Unscheduled) but before the first Visit 2 challenge.

Participants with a missing baseline value will be excluded from the change from baseline analyses.

The mean of replicate assessments at any given time point will be used as the value for that time point.

If baseline data are missing no derivation will be performed and baseline will be set to missing.

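### In Part 2 the planned laboratory change-from-baseline tables cannot show, from scheduled samples, a change that follows the first challenge day and persists to visit 2

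*SAP*

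**What the plan says.** **Sampling.** The Schedule of Activities (Protocol section 1.3.2) places clinical chemistry, haematology and urinalysis in the column headed "Within 1 h before first control challenge" for V1 and, in Part 2, V2. It also marks them at 2 h after the last Substance P (SP) challenge, but a note restricts that sample: "In Part 2, 2 h post last SP challenge at last challenge visit only". Laboratory tests are marked at early withdrawal too. The ECG and vital signs rows carry no such restriction on their 2 h assessment.

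**Baseline.** SAP section 4.1.2 gives Part 2 two baselines, one per visit. For the second, "the Baseline for Visit 2 will be the latest assessment performed after Visit 1 visits (such as Unscheduled) but before the first Visit 2 challenge".

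**Analysis.** SAP section 4.5.3.1 calculates Part 2 laboratory change separately at each visit, "using the visit 1 baseline for visit 1, and visit 2 baseline for visit 2". No comparison of a visit 2 value with the visit 1 baseline is specified.

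**Other data.** Protocol section 8 states: "Repeat or unscheduled samples may be taken for safety reasons or for technical issues with the samples". SAP section 6.2.4 adds: "Unscheduled and withdrawal visits will not be slotted to an analysis timepoint, but they will be considered for worse case and maximum displays".

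**The concern.** The per-visit rule suits ECG and vital signs, which are measured before and after the challenges at both Part 2 visits. It does not suit laboratory data. Visit 1 has a baseline and no scheduled follow-up value, and the first scheduled value after the visit 1 challenges is used only as a new zero point.

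Clinically important laboratory change is a named Part 2 secondary endpoint, listed separately from adverse events (Protocol section 3; SAP section 1.1). If a value moves after the first challenge day and stays moved, the planned change table shows only the small further movement within visit 2. Where the criterion of potential clinical importance (PCI) is itself a change from baseline, the choice of baseline decides whether the participant is flagged.

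**Working it through.** The plan states no figure on this point, so the check is a count of scheduled sample pairs and an illustration.

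**1. Scheduled laboratory samples per Part 2 completer** (Protocol section 1.3.2)

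| Visit | Before challenges | 2 h after last SP | Planned change |
|---|---|---|---|
| 1 | 1 | 0 | none possible |
| 2 | 1 | 1 | visit 2 post minus visit 2 pre |

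**2. Totals for up to 20 completers** (size from SAP section 5)

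- Visit 1 changes: 20 × 0 = 0.
- Visit 2 changes: 20 × 1 = 20.
- Differences between the two pre-challenge samples, collected but not planned as a change: 20 × 1 = 20.
- If both visit 2 samples were also compared with the visit 1 baseline: 20 × 2 = 40 further changes.

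**3. Effect on a change-based criterion.** SAP section 6.2.1.1 flags a haemoglobin fall from baseline beyond 25 g/L. Assumed values for one participant: 150 g/L at visit 1 pre, 124 at visit 2 pre, 123 at visit 2 post.

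- Planned visit 2 change: 123 − 124 = −1. Not flagged.
- Visit 2 pre against the visit 1 baseline: 124 − 150 = −26. Flagged.
- Visit 2 post against the visit 1 baseline: 123 − 150 = −27. Flagged.

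Under the planned rule, a between-visit fall of any size escapes this criterion as long as the fall within visit 2 is at most 25 g/L. The same logic applies to haematocrit (fall of 0.075) and creatinine (rise of 44.2 in the SAP's units). As the table reads, it gives no absolute lower limit for haemoglobin or haematocrit and no absolute limit for creatinine, so for these movements the change criterion is the only PCI flag.

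**4. Effect on the shift table.** SAP section 4.5.3.1 cross-classifies baseline category against worst post-baseline result. If the visit 2 baseline is used, a participant who became Low between visits and stayed Low is counted as unchanged. The SAP does not say which baseline this table uses in Part 2, or whether the visit 2 pre-challenge value counts as post-baseline for visit 1.

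**5. Share of exposure on the first day, for context.** One ascending series is 5 + 15 + 50 + 150 = 220 pmol (Protocol section 6.1). In duplicate, visit 1 carries 8 injections and 2 × 220 = 440 pmol. With the two optional biopsy injections, visit 2 carries the planned 740 pmol (Protocol section 2.3.1), which equals 440 + 2 × 150. The visit 1 share is 440 / (440 + 740) = 37%. Without the biopsy injections it is 440 / 880 = 50%. These shares hold only at the planned concentrations, which may be changed, and dose share does not measure lost safety information.

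**The case against.** A reader might infer that any laboratory change after the first challenge day goes unreported. The documents do not support that:

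- **Withdrawal and unscheduled samples.** Both can supply a value after visit 1, and both enter worst-case displays. This stands, but completers have no scheduled sample of this kind, and an unscheduled value can itself become the visit 2 baseline if it is the latest.
- **Adverse events.** Protocol section 8.2.4 requires clinically relevant laboratory changes to be recorded as adverse events, and section 8.3.1 collects these through the interval between visits. Possible Hy's law values are reported as serious events without reference to a baseline (Protocol Appendix 2). This stands as a reporting route. Apart from the Hy's law rule it depends on the investigator's judgement, and it does not replace a PCI summary.
- **Absolute limits and baseline categories.** Most PCI limits are absolute or multiples of the upper limit of normal, so a new baseline cannot stop them being crossed at the visit 2 post-challenge sample. The shift tables show baseline as Low, within range or High. It would therefore be wrong to say that a persisting abnormality is treated as normal at visit 2. Nor is further change on that day hidden: the within-visit comparison shows exactly that. What is missing is the cumulative change from visit 1.
- **Transient change.** A change that resolves before visit 2 is not absorbed into the new baseline. It is simply not measured.

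A visit-specific baseline is also a sensible way to isolate each challenge day, and the safety analysis is descriptive. The protocol describes local skin effects as transient (section 2.3.1) and the interventions as having a short half-life (section 5.1), which gives little reason to expect laboratory effects lasting days. This lowers the likely yield of the extra comparison. It does not supply the missing one.

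**Conclusion.** The point holds in a limited form. For Part 2 completers and scheduled samples, the visit 1 laboratory change is empty by construction (0 of up to 20), and a change that persists to visit 2 becomes part of the visit 2 baseline, where the planned change tables cannot show it. Flags are directly affected for the three change-based criteria: haemoglobin, haematocrit and creatinine. For the worst-case tables the SAP is silent on the baseline, so the defect there is possible but not established.

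This rests on the schedule as written and on the change criteria following the per-visit rule in SAP section 4.5.3.1. The plan gives no basis for estimating how often such a persistent change would occur. The gap is worth closing because the endpoint is named and the data are already collected, not because a signal is expected.

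**What to change.** In SAP section 4.5.3.1, for Part 2:

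- Also report change from the visit 1 baseline for the visit 2 pre-challenge and post-challenge samples.
- Apply the change-based PCI criteria (haemoglobin, haematocrit, creatinine) and the worst-case shift summaries relative to the visit 1 baseline as well.
- Keep the within-visit 2 change as planned.
- State which baseline each worst-case and hepatobiliary table uses, and whether the visit 2 pre-challenge value counts as post-baseline for visit 1.

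The cost is a short SAP addition and extra table rows, with no new sample or procedure. There is one downside in interpretation. The interval between the challenge visits is not fixed (Protocol section 4.1), so a between-visit change need not be caused by SP, and the added rows should be labelled accordingly. The fix does not recover changes that resolve before visit 2.
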